Research Design and Methods 1 – Overview of Study Design. The proposed study is a multi-site, single-blinded, patient-level randomized-controlled trial of a nurse-coordinated care management intervention for Parkinson’s disease (“CHAPS”) relative to care as usual. Study outcomes will be measured by (1) surveys administered to veterans, to occur at baseline and at 6, 12, and 18 months (and 24 months for the first 204 enrollees), and (2) medical record abstraction in year 4. The primary outcome is adherence to evidence-based guidelines for PD care. Secondary outcomes include: patient health-related quality of life, self-efficacy, and perceptions of care quality. All outcomes will be assessed using intention-to-treat analyses. Three hundred veterans from across five VISN 22 VAs - Greater Los Angeles, Las Vegas, Loma Linda, Long Beach and San Diego - will be recruited and enrolled to enable a final analytic sample (accounting for attrition) of 266. Enrollees will be randomized in a 1:1 ratio to either receive the CHAPS intervention or care as usual. CHAPS intervention components include (1) periodic, structured telephone assessments administered by a nurse care manager specially trained in PD care management at each facility, to identify unrecognized problems (CHAPS Assessment Tool Appendix 1), (2) evidence-based algorithms and protocols to guide care coordination by the nurse care manager (CHAPS Nurse Care Management Manual, Appendix 2), (3) a standalone electronic Microsoft Access database for each nurse care manager, to enable automated triggers of care management and coordination activities, for tracking timeliness of activities (including ‘overdue’ activities) across a registry of his/her patients, and to enable efficient transfer of template clinical reports and care plans (see overall care plan “CHAPS Care Tracker” in Appendix 3) into CPRS (4) veteran and – where appropriate - family involvement in care planning (“My Action Plan” Appendix 4), (5) incorporating self-management tools including My HealtheVet, Patient Education Resource Center and a PD-specific, self-management toolkit including patient notebooks (Siebens Health Care Notebooks) to enrich communication with providers; and an information binder and logs from Davis Phinney (<http://davisphinneyfoundation.org/living-pd/victory-counts>) and; (6) proactive referral mechanisms both within VA and to Parkinson’s disease-specific community resources as needed (referral template in Appendix 5) provide the Veteran has signed the HIPAA granting permission to provide PHI to community organizations as part of the referral process. Outcome variables will be collected by a research assistant interviewer blinded to trial arm status, with three waves of measurement occurring at 6, 12, and 18 months (and 24 months for the first 204 enrollees) after baseline measurement (evaluation survey, Appendix 6).

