a) A nurse care manager uses the CHAPS assessment tool (Appendix 1) to identify PD-problem areas at the initial visit and at 6 month intervals. This assessment tool was developed and pilot-tested among veterans enrolled in the previous NRI pilot-study. The tool will be implemented as an electronic form in Microsoft Access. We will be exploring creation of kiosks in Movement Disorder clinics participating in the study allowing subjects to administer portions of the assessment tool themselves. The assessment tool is based on existing validated and standardized instruments (e.g., PHQ-9 and the WHO-5) currently used throughout the VA. This CHAPS assessment tool is supplemented with assessment tools and questions developed and recognized by the research team as currently in use in other health care settings. Some of these tools and questions have been adapted to fit this patient population. For example, to assess daytime sleepiness, we adapted the Epworth Sleep Scale.

b) Assessment algorithms (triggers) will be developed as Microsoft Access queries to analyze the responses obtained from the assessment tool data to identify problem areas. Queries will be written and automated to identify problem areas. The queries will categorize problems into routine or urgent. For example, a score of 10-17 points on the Epworth Sleep Scale would be categorized as a routine problem, but a score 18 points or greater on the Epworth Sleep Scale would be categorized as an urgent problem. Nurse care managers will be able to conduct queries to determine problems for one patient and problems across his/her group of patients.

Management:

The CHAPS care management processes include re-assessments administered by the nurse over the telephone every 6 months at a minimum and more conversations over the telephone to address identified needs and problems as needed. The nurse will schedule calls with the veteran based on his/her needs. Calls will be adjusted to meet his/her needs. The nurse Care Manager might call the veteran a few days in a row, and then reduce those calls to weekly or monthly calls depending on your

needs. At a minimum, the nurse Care Manager will call veterans once a month to check on the veteran (or less frequently if the veteran requests). Care management tools and protocols include the following:

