3. If the *Preference for Contact Card* is received by the RA and it indicates a preference to be contacted, designated research staff will call the veteran according to the preferences for time and numbers. The staff member will call the veteran and initiate the study *Introductory Script* (Appendix 13). If a preference card is not received by the RA within 14 days, designated research staff will call the veteran to read the study *Introductory Script*. All future contact (assessment interviews and surveys) will occur via telephone according to the preferences for time and numbers indicated by the veteran.

A verbal enrollment and consent process will be used in this study containing all of the elements of informed consent (See Appendix 14). A copy of the verbal consent script will be given to the participant so s/he can reference it during the verbal consent process. The opportunity to consider participating in the study, ask questions and have more time before providing consent will be provided. All procedures must be IRB-approved. If the veteran consents to the study the RA will continue to enroll the veteran using the *Enrollment Script* (Appendix 16)

At the time of consent, baseline, 6, 12 and 18 months (and 24 months for the first 204 enrollees), the potential participant will be asked 3 screening questions for "ability to participate in research". These questions are to determine if the veteran needs help in communicating with the research staff in order to participate in the research study. If the veteran is having difficulty understanding or enunciating over the telephone, we will ask the veteran if she/he would like to have his Care Partner help with this process and involve the Care Partner in a dialog to answer the research questions administered by research staff to the veteran subject. If at any time the veteran is not able to take part in a dialog with the research nurse or interviewer -- even with the Care Partner present -- then we will try again within two weeks. If the veteran is still unable to participate in a dialog

over the telephone even with the help of his Care Partner, then we will (1) NOT enroll the veteran (if not already enrolled in the study), or (2) remove the enrolled veteran subject from the study and transfer the veteran to usual care for his/her care to be continued.

Figure 4. Flow diagram of steps in the recruitment, enrollment, intervention and evaluation in the RCT of CHAPS intervention

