Veteran survey: telephone interview (Appendix 6). Telephone surveys will be administered to all study participants by trained research assistants. A baseline interview of about 30-40 minutes duration will be administered prior to randomization. Three follow-up telephone interviews will also be about 30-40 minutes duration. Each will be administered at 6, 12, and 18 months (and 24 months for the first 204 enrollees) after enrollment by a research assistant who will be blinded to randomization status. Procedures to promote retention will include allowing the interviews to be broken into multiple sessions, and scheduling at times that are convenient for the veteran. Study participants will be provided \$25 per survey as recognition for their time. SSNs will be obtained from CPRS to process subject payment. SSNs will be included in the Patient Registry which will be stored in an Excel file, and will be placed in a password protected file on a VA desktop computer that is backed-up on the secure server at the VA Sepulveda HSR&D COE. Occasionally Veterans move and/or change their telephone numbers. In the event the study RA is unable to reach an enrolled participant by telephone in order to administer the Evaluation survey (s), an “Unable to Reach for Survey Letter” (Appendix 17) will be mailed to the enrolled participant. The letter aims to offer a participant the opportunity to continue with the study and to complete the Evaluation surveys at baseline, 6, 12 and 18 months (and 24 months for the first 204 enrollees). This letter will be mailed in the event the participant’s phone number has been identified as either no longer in service, appears disconnected, or is now an incorrect number for the respective participant.

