Research Design and Methods 7 – Strategy for Data Analysis. All analyses will follow the intention-to-treat principle in that participants are included in the analyses regardless of the level of exposure to the intervention activities. In order to accomplish this analysis in patients who drop out of the study, we will employ a conservative imputation method such as last-value-carried-forward (LVCF). We will consider a P value less than or equal to 0.05 as statistically significant.

Specific Aim #1. Primary Outcome: Guideline Adherence. Guideline adherence will be determined by de-identified medical record and caregiver survey data. Outcomes are expressed as a percentage of applicable guidelines followed, which can be treated as continuously-scaled. In Table 4 of this application are examples of PD indicator process measures. Overall guideline adherence will be calculated as the mean percentage of eligible guidelines per patient that was adherent. Each of the 38 guidelines will also be analyzed individually.

All multivariate analyses will be preceded by bivariate analyses to describe relationships between key variables. First, descriptive statistics comparing the two arms on sociodemographic and clinical characteristics

(such as duration of PD) and on study outcome measures at baseline, using two-sample t-tests for continuous variables and χ^2 tests for categorical variables. We'll also compare baseline characteristics between participants who complete follow-up surveys and participants who do not complete follow-up surveys. Participants who do not finish the 18-month follow-up (or 24 months for the first 204 subjects; see below) due to bereavement or loss to follow-up will be excluded from the analyses but sensitivity analyses will include these participants.

An intention-to-treat analysis on all guideline adherence over time will be conducted using linear regression (or logistic regression when analyzing guidelines individually) with sampling weights using the sandwich variance estimator (robust variance estimator and Huber correction)⁵⁴⁻⁵⁵ as implemented in Stata, version 11. Intervention status, indicator variables for site and corresponding baseline measure will be included as independent variables in all models. Other potential important covariates will be selected in advance of data analysis to be included in the model.

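### Randomised veterans who can no longer hold a telephone dialog are removed from the study, and the plan does not keep them or their record data in the intention-to-treat analysis

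*Combined protocol and SAP*

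**What the plan says.** - **Removal rule** (Research Design and Methods 6, Recruitment and Enrollment/Consent Processes). The trigger reads "If at any time the veteran is not able to take part in a dialog with the research nurse or interviewer". The Care Partner may help, and contact is tried again within two weeks. If there is still no dialog, staff "remove the enrolled veteran subject from the study and transfer the veteran to usual care for his/her care to be continued".
- **Scheduled screen** (same section). Three ability questions are asked at consent, at baseline and at every follow-up survey, on the same dates in both arms.
- **Surveys** (Veteran survey). "A baseline interview of about 30-40 minutes duration will be administered prior to randomization". Each follow-up survey is given "after enrollment by a research assistant who will be blinded to randomization status".
- **Nurse calls, intervention arm only** (Methods 2, Management). "At a minimum, the nurse Care Manager will call veterans once a month to check on the veteran", or less often if the veteran asks.
- **Intention-to-treat** (Methods 1 and 7). "All outcomes will be assessed using intention-to-treat analyses", and in Methods 7 "participants are included in the analyses regardless of the level of exposure to the intervention activities".
- **Non-finishers** (Methods 7). Dropouts are to be imputed, for example by last value carried forward. The same section excludes from its analyses those who do not reach the end through bereavement or because they were lost, and brings them back only in sensitivity analyses. Attrition weights are added for survey outcomes; demographics are the only predictors named.
- **Record data** (Methods 6, Missing-data). Chart and administrative data are expected to have no gaps.
- **Attrition** (Methods 4, sample size). The causes named are disenrolment and death.

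**The concern.** The trial admits all stages of Parkinson's disease and expects a mean age of about 75, so some participants can be expected to lose the ability to talk by telephone during 18 to 24 months. Removing them after randomisation is informative loss: the reason is plausibly tied to disease progression, and so to quality of life, self-efficacy, perceptions of care and the survey-based part of guideline adherence.

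Part of the loss is also unnecessary. The chart-based part of the primary outcome and the Data Warehouse utilisation data need no dialog. No section says whether a removed veteran counts as lost to follow-up, whether the chart is still abstracted, or whether utilisation is still extracted. If removal ends these too, the comparison is no longer of the groups as randomised.

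**Working it through.** **1. The plan's own figures.** Table 3 reproduces. A two-sample t-test with SD 1, two-sided alpha 0.05 and 90% power needs 235, 173 and 133 per arm at effect sizes 0.3, 0.35 and 0.4. The planned analytic sample is 266 of 300, which is 88.7% retention and an allowance of 300 − 266 = 34 losses. This point disputes none of these figures.

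**2. What removal does to each data source.**

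| Source | Needs a dialog? | Stated handling after removal |
|---|---|---|
| Survey outcomes and survey part of adherence | Yes | Imputation, exclusion and weighting all appear in Methods 7 |
| Chart part of adherence | No | None stated; data expected complete |
| Data Warehouse utilisation and cost | No | None stated; data expected complete |

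The weights do not reach the last two rows. Weights built mainly on demographics may not capture loss driven by disease progression. Carrying the last value forward uses a score from before the decline.

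**3. Opportunities for removal by arm.** This step applies only if the undefined term research nurse includes the nurse care manager.

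- Usual care: 3 surveys in 18 months, or 4 in 24.
- Intervention: the same surveys plus about 18 monthly calls. In the 24-month cohort the intervention gap of more than 6 months leaves at most about 24 − 6 = 18 calls at that pace.
- Lasting inability is found by the next survey in either arm. Cumulative removal is then about equal, and intervention patients are removed up to about 6 months earlier.
- For a temporary episode, assume it lasts D months and must still be present at a retry 0.5 month later. The chance of removal is min(1, (D − 0.5)/1) with monthly contact and min(1, (D − 0.5)/6) with 6-monthly contact.

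| D (months) | Monthly | 6-monthly | Ratio |
|---|---|---|---|
| 1 | 0.50 | 0.083 | 6.0 |
| 1.5 | 1 | 0.167 | 6.0 |
| 2 | 1 | 0.25 | 4.0 |
| 3 | 1 | 0.417 | 2.4 |
| 6.5 | 1 | 1 | 1.0 |

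**4. Possible bias if only retained participants are analysed.** Assumptions: 150 per arm; the same share r_I would fail a dialog in each arm; all of them are removed in the intervention arm but only r_C in usual care; those who fail score δ = 0.5 to 1 SD worse. The retained usual-care group then still holds a share (r_I − r_C)/(1 − r_C) of such patients, so

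bias = δ (r_I − r_C)/(1 − r_C), with SE = √[1/(150(1 − r_I)) + 1/(150(1 − r_C))].

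For 6% against 3% and δ = 1: bias = 0.03/0.97 = 0.031; SE = √(1/141 + 1/145.5) = 0.118; the two-sided type I error is 0.058.

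| Removal, intervention against usual care | Bias (SD), δ = 0.5 to 1 | Type I error |
|---|---|---|
| 4% against 2% | 0.010 to 0.020 | 0.051 to 0.054 |
| 6% against 3% | 0.015 to 0.031 | 0.052 to 0.058 |
| 10% against 5% | 0.026 to 0.053 | 0.056 to 0.072 |
| 11.3% in both arms | 0 | 0.050 |

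The first and third rows mean 6 + 3 = 9 and 15 + 7.5 = 22.5 people removed, or 26% and 66% of the 34 allowed losses.

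**5. Cost window.** If extraction stopped at removal, an affected intervention patient could lose up to about 6 of 18 months more than a comparable control, in an analysis that compares total cost per participant.

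**The case against.** The removal rule governs participation, not the analysis set. It has two safeguards, the Care Partner and the retry, that should keep many patients with speech or cognitive decline in the study. The plan also provides imputation, weights and sensitivity analyses. Record collection is retrospective, and no section says that it stops at removal. The consent script and the human-subjects section are not in the supplied text, so continued record access cannot be judged. All of this stands, and it limits the point. It does not settle how a removed participant is analysed, and sensitivity analyses do not repair a main analysis that excludes randomised patients.

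A reader might infer from the monthly calls that removal is more frequent in the intervention arm and flatters its results. The documents do not support this. Research nurse is undefined, although nurse care managers are the only nurses described as telephoning enrolled veterans. The formal screen falls on the same dates in both arms, with blinded interviewers at follow-up. Lasting inability is found by the next survey in either arm, so an excess would need temporary episodes or a death before that survey.

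The direction is open as well. Nothing shows that those removed meet a smaller percentage of applicable indicators. If their charts are kept, earlier transfer to usual care would dilute the intervention effect rather than inflate it.

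**Conclusion.** The concern holds in a limited form. Followed as written, the plan removes randomised veterans for a reason plausibly tied to disease progression. If they count as lost to follow-up, which is the natural reading, it then leaves them out of the main analyses. That conflicts with its own intention-to-treat statements and, if abstraction or extraction stops, with its expectation of complete record data. The consent, missing-data and analysis sections must be reconciled.

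If nurse care manager calls count, the intervention arm has more opportunities for removal and earlier removal, by up to about 6 months. More frequent removal is possible but not established, and the direction of bias is uncertain.

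The likely size is small: about 0.01 to 0.05 SD, at most about 13% of the 0.4 SD design effect (0.053/0.4), and zero under equal removal in the same model. The removal rates and the 0.5 to 1 SD deficit are assumptions, since the documents give neither. The change should be made because it is cheap and protects the randomised comparison, not because a large bias has been shown.

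**What to change.** State that, for data purposes, a failed dialog ends survey collection only:

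- The participant stays in the analysis set as randomised.
- Chart abstraction and Data Warehouse extraction continue to the planned 18 (or 24) months in both arms, subject to the consent given and IRB agreement.
- Missing surveys are handled by the main missing-data method, which Methods 7 should name as one method.
- Removals are reported by arm, date and who detected them.

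This concerns data retention only; the clause on transfer of care is not addressed.

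The cost is a short amendment and IRB confirmation, with no new assessments and no change in sample size. The December 2015 schedule places abstraction in the last two project periods, so record data for veterans already removed may still be recoverable if consent allows.
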